## **B.** Specific Aims

Primary:

- 1. To estimate the proportion of additional infectious etiologies of febrile illness among patients presenting with an undifferentiated fever of 3 to 21 days duration.
- 2. To compare the use of antimicrobials in patients with undifferentiated fever in whom additional microbiological tests have been performed versus patients with clinical diagnosis alone.

Secondary:

- 3. To evaluate the appropriateness of the empiric antibiotic therapy based on clinical diagnosis alone and after laboratory confirmation.
- 4. To estimate the correlation between clinical diagnosis with laboratory diagnosis in patients with undifferentiated fever.
- 5. To compare the outcome among patients whose treatment is based on microbiological diagnosis compared to the patients whose treatment is based on clinical diagnosis alone.

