## j. Data Collection, Data Analysis and Sample Size

Demographic, clinical, radiological, and laboratory data will be collected and entered into a password protected database. To minimize the errors, data will be directly entered into the database using REDCap Database questionnaires.

Data analysis will include the followings:

- 1. Demographics and baseline characteristics of patients will be analyzed and compared between the two groups.
- 2. Clinical diagnosis and laboratory confirmation of diagnosis will be used to estimate the proportions of various infectious etiologies of febrile illness in patients presenting with a febrile illness of 3-21 days duration. (Specific aim-1)
- 3. Number, type, dose and duration of antimicrobials used to treat the patients will be collected and compared between the two groups: clinical diagnosis alone versus clinical plus microbiological diagnosis. (Specific aim 2)
- 4. Appropriateness of the empiric antibiotic therapy will be determined by an independent physician expert after the laboratory confirmation of the diagnosis. Comparison between the two groups (clinical diagnosis vs. microbiological diagnosis) will be done by calculating the proportion of cases who received appropriate antibiotics divided by the total number of cases for whom empiric antibiotics were administered. (Specific aim-3)

- 5. Pretest probability for clinical diagnosis and posttest probability after laboratory-based diagnosis will be calculated and correlated for bacterial, rickettsial, viral infections versus other causes of fever. (Specific aim-4)
- 6. Clinical outcomes will be compared for patients whose treatment is based on clinical diagnosis alone (Group 1) versus the patients whose treatment is based on clinical plus microbiological diagnosis (Group 2). Composite Positive outcome (complete or partial recovery) and Negative outcome (in-hospital death) will be compared between the two groups. (Specific aim-5)

Demographics and baseline characteristics of patients will be expressed in percentages, means±SD, 95% confidence intervals, and/or median±IQR, as appropriate. Proportions will be compared between the two groups with Chi-square tests. Numerical variables will be expressed as Means/SD/95% confidence intervals and Median/IQRs, whereas Student T test or Mann-Whitney test, respectively, will be used for statistical comparisons. Alpha will be set at 95% (level of significance, p <0.05).

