For Specific aims 2 and 3, total daily defined dose (DDD) for each antimicrobial agent received by patients will be calculated following WHO guidelines. The total DDD, number of antibiotics, and Duration of antibiotics used will be compared between the groups by calculating Means/SD/95% confidence intervals. Similarly, appropriateness of antibiotic uses will be tested with cross-tabulation using Chi-square analysis.

For specific aim 4, pre-test probability and post-test probability will be determined by both using standard calculations and using Fagan's Nomogram. Correlations between pre- and post-test probabilities for bacterial, rickettsial, viral vs. other causes will be evaluated.

For specific aim 5, the hazard ratio using the Cox proportional hazard model will be calculated to compare the outcomes between the groups. Since multiple factors, such as comorbidities, severity of illness at baseline, type of infection and host immune status, can influence the outcomes, adjustment for these factors will be considered during the univariate and multivariate outcome analyses. Updated Charlson comorbidity index (Quant et al.) will be calculated and used for comparison between the groups [15]. Similarly, qSOFA will be used to stratify the patients by severity of infection [16].

REDCap (Research Electronic Data Capture) software will be used for questionnaire and database entry. SPSS version 25 (IBM, USA) will be used for statistical analysis.

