# C. Clinical and Laboratory Questionnaire (Standard of Care Evaluation for all participants)

No.	Questions/ Variables	Data / value	Unit
	BASELINE CLINICAL DATA		
C1	Duration of fever	No. of days	
C2	Clinical Diagnosis		
C3	System involvement	RTI, GI, UTI, CVS, CNS,	
		SSTI, Blood, Sepsis,	
		Lymphatic, Other	
C4	Comorbidities	None, DM, HTN,	
		COPD/chronic	
		pulmonary dis., CHF,	
		MI, PVD, CLD/Liver	
		failure, PUD, CVA,	
		hemiplegia, dementia,	
		CTD, AIDS, solid	
		tumor, lymphoma,	
		leukemia, other	
C5	Temperature in Celsius (baseline at		Celcius
	presentation)		
C6	BP (baseline at presentation)		mmHg
C7	Pulse (baseline at presentation)		per min.
C8	Resp rate (baseline at presentation)		per min.
C9	SaO2 (baseline at presentation)		%
C10	WBC (baseline at presentation)		per cumm
C11	ANC (baseline at presentation)		per cumm
C12	ALC (baseline at presentation)		per cumm
C13	AEC (baseline at presentation)		per cumm
C14	Hgb (baseline at presentation)		g/dL
C15	Plt		per cumm
C16	CRP		
C17	ESR		per hour
C18	Cr		
C19	ALT		
C20	AST		
C21	UA: pus cells		
	MICROBIOLOGICAL DATA		
M1	Blood culture result	Organism name	
M2	Urine culture result	Organism name	
M3	Sputum culture result	Organism name	
M4	Pus culture	Organism name	
M5	GeneXpert	Positive/negative	
M6	Dengue serology	NS1, IgM, IgG	
M7	Scrub typhus	Positive/negative	

M8	Malaria RDT	P falciparum, P vivax,
		other
M9	Kala Azar	Positive/negative
M10	Brucella	Positive/negative
M11	MTB	Positive/negative
M12	Leptospirosis	Positive/negative
M13	Hepatitis A	IgM
M14	Hepatitis E	IgM
M15	Hepatitis B	HBsAg
M16	Hepatitis C	HBC Ab
M17	HIV	
M18	Other test results ()	
M19	Other test results ()	
M20	Other test results ()	
	RADIOLOGICAL DATA	
R1	X-ray finding	Consolidation,
		Infiltrates, Pleural
		effusion, CHF, ARDS,
		other
R2	CT Chest	Consolidation,
		Infiltrates, Pleural
		effusion, CHF, ARDS,
		other
R3	CT Abdomen	Hepatomegaly,
		pancreatitis,
		Cholecystitis, Gall
		stone, Ascites,
		appendicitis, typhlitis,
		intrabdominal
		abscess,
		lymphadenopathy,
		other
R4	USG Abdomen	Hepatomegaly,
		pancreatitis,
		Cholecystitis, Gall
		stone, Ascites,
		appendicitis, typhlitis, intrabdominal
		abscess,
		lymphadenopathy, other
R5	CT/MPI ckull	
KO	CT/MRI skull	Abscess, Meningitis,
		Encephalitis,
		parameningeal focus, other
		otilei

R6	Echocardiogram	Valvular vegetation,
		Pericardial effusion,
		other
	ADDITIONAL SEROLOGICAL EVALUATIONS	Results
	(for Group B patients only)	
D1	Murine typhus	Positive, negative, NA

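### Primary aim 2 and aim 3 are compared without covariate adjustment, although baseline predictors are collected on every patient: a loss of precision, not of validity

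*Protocol*

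**What the plan says.** Section 4.B of the protocol lists aim 2 under the primary aims: "To compare the use of antimicrobials in patients with undifferentiated fever in whom additional microbiological tests have been performed", against patients with clinical diagnosis alone.

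Section 5.j gives the analysis. For the antimicrobial measures, "The total DDD, number of antibiotics, and Duration of antibiotics used will be compared between the groups by calculating Means/SD/95% confidence intervals". The tests come from the general paragraph just before. For proportions, "Proportions will be compared between the two groups with Chi-square tests"; for numerical variables, "Student T test or Mann-Whitney test, respectively, will be used for statistical comparisons". Aim 3 (appropriateness of therapy) is a cross-tabulation with chi-square. No covariate or stratification factor is attached to aim 2 or aim 3.

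Adjustment is mentioned once, in the aim 5 paragraph that introduces the Cox model. It notes that comorbidity, severity at baseline, type of infection and immune status can influence outcome, and says that "adjustment for these factors will be considered during the univariate and multivariate outcome analyses". In the same paragraph the Charlson index "will be calculated and used for comparison between the groups", and "qSOFA will be used to stratify the patients by severity of infection".

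In Appendix 1, part C of the questionnaire is headed as "Standard of Care Evaluation for all participants". It records fever duration, comorbidities, vital signs, WBC, CRP and other markers. The qSOFA and Charlson tables in part D are not limited to one arm. Only the additional serology is restricted to Group B.

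**The concern.** How many antimicrobials a febrile inpatient receives, and for how long, plausibly depends on how ill the patient is at presentation. The protocol itself accepts that severity and comorbidity influence outcome, but it uses that information only for a secondary aim. The primary comparison gets the less precise analysis.

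With adjustment, the part of the outcome variance explained by baseline data leaves the standard error, at no cost in patients. That matters in a single-centre study whose size, by its own limitations section, is set by budget. Naming the covariates in advance also fixes the choice before any baseline imbalance between arms has been seen.

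**Working it through.** **Inputs from the protocol.** Sample-size section: antimicrobial use 90% versus 75%, 80% power, 97 per arm (labelled there as aim 1, although antimicrobial use is aim 2 in section 4.B), and 117 per arm after a 20% allowance. Section 5.j: significance level 0.05. The sidedness is not stated, but a two-sided test reproduces the stated figure.

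**Input assumed.** R², the share of outcome variance explained by the baseline covariates. The protocol gives neither R² nor a standard deviation for DDD or duration, so a range of 0 to 0.30 is shown.

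**Step 1: reproduce the plan's figure.** Two proportions, unpooled variance:

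n = (0.90×0.10 + 0.75×0.25) × (1.960 + 0.842)² / 0.15² = 0.2775 × 7.849 / 0.0225 = 96.8, so 97 per arm. Then 97 × 1.2 = 116.4, so 117. Both match. The trial is sized for an unadjusted comparison, and the sizing does not depend on adjustment.

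**Step 2: effect of adjustment on a continuous outcome.** With 97 analysed per arm, the difference detectable with 80% power is (1.960 + 0.842) × √(2/97) = 0.402 SD. Adjustment multiplies the standard error by √(1−R²), so

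power = Φ(2.802/√(1−R²) − 1.960).

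| Assumed R² | SE reduced by | Power | Detectable difference (SD) | n per arm for 80% power |
|---|---|---|---|---|
| 0 | 0% | 80% | 0.402 | 97 |
| 0.05 | 2.5% | 82% | 0.392 | 93 |
| 0.10 | 5.1% | 84% | 0.382 | 88 |
| 0.20 | 10.6% | 88% | 0.360 | 78 |
| 0.30 | 16.3% | 92% | 0.337 | 68 |

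Worked line for R² = 0.20: 2.802/√0.80 = 3.132; 3.132 − 1.960 = 1.172; Φ(1.172) = 0.879. The equivalent gain in patients is 1/(1−R²) − 1, that is 5%, 11%, 25% and 43% for the last four rows.

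These figures apply directly to DDD and duration, and approximately to the number of agents.

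**Step 3: the binary endpoint.** For 90% versus 75% the same formula holds only if the estimate is a standardised (marginal) risk difference, with R² taken on the risk scale. As an illustration, assume one normally distributed baseline score with a logistic relation to antimicrobial use in each arm. A score with AUC 0.65, 0.70 or 0.75 then gives R² of about 0.05, 0.08 or 0.14, and power of about 82%, 83% or 85%. R² = 0.20 needs an AUC of about 0.80.

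**Step 4: are the covariates truly baseline?** In part C of the questionnaire, temperature, blood pressure, pulse, respiratory rate, SaO2, WBC and differential counts, and haemoglobin are marked as baseline at presentation. CRP (item C16) has no time point, and neither does the qSOFA table in part D. Section 5.f places collection of standard-of-care results before the additional tests, but the form does not tie these two items to presentation.

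**The case against.** **The plan is valid and coherent as it stands.** This is correct. Randomisation makes the unadjusted comparison unbiased, and the sample size was worked out for it. A reader might infer that chance imbalance in severity biases the antimicrobial contrast. The documents do not support that: such imbalance is random variation that the standard error and the significance level already cover.

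**The size of the gain has no source in the documents.** Also correct. The exclusions (immunocompromise, neutropenia, known HIV, recent hospital stay) narrow the spread of risk, and few ward patients may score on qSOFA, so R² could be near zero. A reader might take 92% power, or 43% more patients, as the gain on the endpoint for which the trial was sized. That is not supported: the 80% power belongs to a binary endpoint, and the top of the range would need a very strong predictor. The protocol states no power for DDD or duration.

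**Covariate lists belong in a SAP.** Often so, and one may exist. But the protocol does more than stay silent: it names unadjusted tests for these aims. The point is about that stated choice.

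**The sentence on multivariate outcome analyses might also cover aim 2**, since section 5.i counts antimicrobial de-escalation among patient outcomes. This does not stand. The sentence sits inside the aim 5 paragraph and follows directly from the Cox model.

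**The plan invites covariates picked after imbalance is seen.** A reader might infer this from the planned baseline comparison between groups. No passage says that covariates for aim 2 will be chosen that way. Prespecification would simply close the question.

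**Conclusion.** The point holds as a missed gain in efficiency on a primary aim. The named tests for aims 2 and 3 are unadjusted, adjustment is tied to secondary aim 5 only, and suitable baseline data are already collected on everyone. There is no bias and no error in the sample size.

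The gain rests wholly on an assumed R². For DDD and duration it runs from nothing at R² = 0 to 92% power in place of 80% at R² = 0.30. For the binary endpoint, 82% to 85% is a fairer expectation under the illustrative AUCs of 0.65 to 0.75, and only with a standardised risk difference. Both statements assume that every covariate is measured before randomisation. The form does not yet secure this for qSOFA and CRP.

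**What to change.** In section 5.j, state that aims 2 and 3 are estimated by regression on randomised arm, adjusted for a short prespecified list of pre-randomisation covariates: for example qSOFA, updated Charlson score and fever duration, plus CRP or WBC at presentation.

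- Total DDD and duration: linear model with robust standard errors.
- Number of agents: count model.
- Proportions, including appropriateness in aim 3: standardised risk difference from a logistic model.
- Unadjusted comparison: keep as a sensitivity analysis.

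State in the protocol and on the form that qSOFA and CRP are the values at presentation, before randomisation. Do not carry over type of infection from the aim 5 list: the randomised tests partly determine it, so it is not a baseline variable.

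The cost is a paragraph in section 5.j, a time point added to two form items, and a little extra analysis. No extra patients or tests are needed. The change is best made before any data are examined by arm, and so before the interim analyses planned at 25% and 50% of enrolment.

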#### c. Inclusion criteria

- 1. Age 16 years or older
- 2. Documented fever (T ≥100.4F or ≥38C) of 3 days to 21 days duration
- No obvious diagnosis found on the basis of clinical, radiological, or initial routine laboratory tests\*
- 4. Admitted to the medical unit of hospital
- 5. Signed ICF (informed consent form)

(\* Initial routine laboratory tests for an etiologic diagnosis of febrile illness work up includeblood and urine cultures, malaria RDT or thick and thin smears, sputum culture and GeneXpert for MTB (if suspected on chest X-ray), and serologies for scrub typhus, dengue, Dengue, Scrub typhus, Leptospirosis, Brucellosis, Kala azar, and HIV, as indicated based on clinical picture)

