## Additional Evaluations for the Study

For patients without an obvious cause of fever and an inconclusive work up after standard of care evaluations, additional serological tests as a part of undifferentiated febrile illness work up will be performed, including:

- a. Clinical evaluation: includes thorough history and physical examinations based on a standard questionnaire and data collection tool
- b. Additional Microbiological Evaluations: If above listed laboratory and microbiological tests do not indicate a conclusive diagnosis, the patient's blood will be processed for additional Serological tests as a part of undifferentiated febrile illness work up. These tests will help to establish diagnosis of the following infections:
  - Murine typhus
  - Bartonellosis
  - Q-fever
  - Chikungunya
  - 7ika
  - Japanese B encephalitis
  - West Nile virus
- 5. Use of antimicrobials in the patients with and without an etiological diagnosis and their outcome at the time of discharge from the hospital will be recorded.
- g. Laboratory Methods

For the purpose of the study, following samples will be collected from 50% of randomly assigned patients for additional microbiological testing.

- 1. Blood cultures, 2 sets from 2 different sites from all study patients (20 mL total)
- 2. Serum samples for serological testing (4 mL)

After obtaining appropriate consent, total 25 mL blood will be collected from each patient assigned to the additional testing arm. Blood samples will be cultured in liquid media and held in the incubator for 7-days.

Urine will be taken to the lab for routine examination and culture will be performed only if there are >10 pus cells or patient reports urinary symptoms.

Gram stain, AFB stain and Genexpert will be performed on sputum samples.

As a part of routine febrile illness work up, the serum samples will be tested for HIV, scrub typhus, dengue, leptospirosis, brucella, malaria, and kala azar.

Additional serum sample will be processed for further serological testing for Chikungunya, Zika, *Coxiella burnetii* (Q-fever), *Bartonella henselae* (Bartonellosis), *Rickettsia typhi* (murine typhus), Japanese B encephalitis, and West Nile virus using ELISA and/or Rapid Diagnostic Test (RDT), as applicable. Although molecular tests have a higher sensitivity and specificity, molecular testing has not been planned for this study because of the budget limits.

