#### Patient should meet none of the Exclusion criteria below:

No.	Question	Yes	No
b7	Children (younger than 16 years in age)**		
b8	Fever of less than 3 days or more than 21 days duration		
b9	Outpatients		
b10	Patients being discharged from Emergency Room		
b11	Immunocompromised patients		
b12	Neutropenia (ANC <500 per cumm)		
b13	Known case of HIV infection		
b14	Hospital admission for 48-hours or longer within past 30 days		
b15	Patient does not meet any of the above exclusion criteria		

(\*\*Children under 16 years will be excluded since they have different causes of febrile illnesses requiring a different set of lab tests which is beyond the scope of this study.)

If patient meets all of Inclusion criteria and none of the exclusions, proceed with patient consent followed by randomization and enrollment.

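### Aim 5 may adjust for type of infection without limiting it to pre-randomisation information; if taken from laboratory diagnosis, it depends on the arm and biases the comparison

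*Protocol*

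**What the plan says.** Aim 5, a secondary aim, compares outcome between patients treated on clinical diagnosis alone and patients treated on clinical plus microbiological diagnosis. Section 5.j states that "the hazard ratio using the Cox proportional hazard model will be calculated to compare the outcomes between the groups". It then lists factors for which adjustment is an option: "comorbidities, severity of illness at baseline, type of infection and host immune status, can influence the outcomes, adjustment for these factors will be considered". The words *at baseline* attach to severity only: "severity of illness at baseline, type of infection".

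Four other places bear on what type of infection can mean.

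- **Entry.** Section 5.c requires "No obvious diagnosis found on the basis of clinical, radiological, or initial routine laboratory tests".
- **Order of events.** After the eligibility checks, Appendix 1 B says to "proceed with patient consent followed by randomization and enrollment".
- **Who is tested.** Section 5.g says "following samples will be collected from 50% of randomly assigned patients for additional microbiological testing". On the data form, items D1 to D7 (the seven added serologies) are marked "for Group B patients only".
- **How infections are typed.** The only explicit typing is in Section 5.j, item 5, for aim 4, where pre-test and post-test probabilities are "correlated for bacterial, rickettsial, viral infections versus other causes of fever". The post-test side is the laboratory-based diagnosis.

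The data form has no field called type of infection. Arm labels differ between sections (Groups 1 and 2 in Section 5.j, Groups A and B in Appendix 1). Group B is the added-testing arm.

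**The concern.** Comorbidity and baseline severity are fixed before allocation and can be measured alike in both arms. A laboratory-based infection type is not. The true infection precedes randomisation, but its ascertainment follows it and depends on the arm. A patient with murine typhus, Q fever or chikungunya can be typed in Group B and remains undetermined in Group A.

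Two things are then at stake. First, adjustment compares Group B's undetermined patients, from whom the newly diagnosed have been removed, with Group A's undetermined patients, who still include them. That can create an arm difference where none exists. Second, diagnosis is the route by which testing is meant to change treatment and outcome. Conditioning on it takes out part of any real effect. Randomisation protects the unadjusted comparison, and adjusting for a variable that the intervention changes gives up that protection.

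**Working it through.** **1. The plan's own figure for this comparison.** The sample size section gives 79 per arm for 60% versus 80% with 80% power. With unpooled variance and two-sided alpha 0.05 (the protocol gives p < 0.05 without sidedness):

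n = (1.96 + 0.8416)² × (0.6×0.4 + 0.8×0.2) / 0.2² = 7.849 × 0.40 / 0.04 = 78.5, rounded up to 79.

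The figure reproduces and is not in dispute.

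**2. Expected imbalance in recorded type.** The same section assumes that identification of causative agents rises from 30% to 50%. Take these as the shares with a recorded type in Groups A and B. Per 100 patients, Group A then has 70 undetermined and Group B has 50. Group A's 70 include 20 who would have been typed in Group B (20/70 = 28.6%).

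**3. Undetermined stratum, no true arm effect.** The documents give no risks by infection type, so the risks below are assumptions. Let r_d be the poor-outcome risk in infections that only the added tests detect, and r_o the risk in those who stay undetermined in either arm.

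- Group A risk = (20 × r_d + 50 × r_o) / 70
- Group B risk = r_o

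| r_d / r_o (assumed) | Group A | Group B | Ratio B/A |
|---|---|---|---|
| 2% / 10% | 5.4/70 = 7.7% | 10% | 1.30 |
| 20% / 40% | 24/70 = 34.3% | 40% | 1.17 |
| 40% / 20% | 18/70 = 25.7% | 20% | 0.78 |

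Every ratio should be 1. The direction depends on whether the newly detectable infections are milder or more severe than the rest. These are ratios within one stratum, not the adjusted arm effect, so a whole-model check is needed.

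**4. Full Cox model, no true arm effect.** Each scenario simulates 20,000 patients, split equally. Half have an identifiable infection; type is recorded for 30% of Group A and 50% of Group B. Event times are exponential with hazard 0.1 per day, multiplied by an assumed type hazard ratio in the identifiable half, and follow-up is cut at 14 days.

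| Type HR (assumed) | Arm HR, unadjusted | Arm HR, adjusted for recorded type | Adjusted / unadjusted |
|---|---|---|---|
| 0.5 | 1.007 | 1.164 | 1.16 |
| 0.67 | 0.996 | 1.068 | 1.07 |
| 1 | 0.971 | 0.969 | 1.00 |
| 1.5 | 1.014 | 0.944 | 0.93 |
| 2 | 1.026 | 0.919 | 0.90 |
| 3 | 1.002 | 0.872 | 0.87 |

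The unadjusted values differ from 1 by simulation noise only. The last column removes that noise. Bias is nil when type is not prognostic and grows as type becomes more prognostic.

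**The case against.** **The adjustment is not fixed.** A reader might infer that the aim 5 model will adjust for type of infection. The text does not support that: it says only that adjustment is to be considered, and the final covariate list could be settled in a statistical analysis plan. This stands, and it makes the risk conditional. It does not remove the point. The protocol names this variable as a candidate, and an analyst who follows the text may fit it.

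**Type of infection may mean something recorded at baseline.** A reader might also infer that the covariate cannot be derived alike in both arms. That is too absolute. Appendix 1 C collects clinical diagnosis (C2) and system involvement (C3) as baseline data for all participants, and either could serve. The protocol does not say so, however, and the one typing it spells out rests on laboratory results, though for aim 4. The text is open to both readings and needs to choose one.

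**The reach is limited.** Aim 5 is secondary. Section 5.j, item 6 plans a direct comparison of the composite outcome, and the Cox hazard ratio is stated before adjustment is mentioned. An unadjusted comparison free of this bias is therefore planned. This stands.

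**The bias may be small beside sampling error.** Suppose 20% of patients have risk 2% and the rest 10%. Overall risk is 0.2×0.02 + 0.8×0.10 = 8.4%, or 9.8 deaths among 117. The standard error of the log risk ratio is √[2 × (1/9.8 − 1/117)] = 0.43, so the 95% interval spans a factor of exp(1.96 × 0.43) ≈ 2.3 either way. This bears on severity, but a bias that can be avoided by editing the text should not be kept on that ground.

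**Conclusion.** The point holds in conditional form. If type of infection is taken from laboratory diagnosis, it is a post-randomisation variable ascertained differently by arm. Adjusting for it then biases the aim 5 comparison whenever type is prognostic, and the protocol's own sentence asserts that it is.

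With the protocol's 30% and 50% identification rates and no true effect, the adjusted hazard ratio lies between about 0.87 and 1.16 for assumed type hazard ratios of 3 to 0.5. The size rests on those assumed hazard ratios, on exponential event times, and on reading 30% and 50% as the recorded shares in the two arms.

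A reader might infer that the adjustment would make testing look harmful. The documents do not support a direction, because they give no outcome by infection type and the sign reverses with the assumption. Neither primary aim is affected. The flaw is worth correcting because a variable open to this use is named in the text, not because a biased result is certain.

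**What to change.** In the aim 5 paragraph of Section 5.j:

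1. Remove type of infection from the factors for adjusting the arm comparison, or replace it with a pre-randomisation variable recorded alike in both arms (clinical diagnosis C2 or system involvement C3).
2. State that all adjustment covariates are measured before randomisation and identically in both arms, for example the Charlson index, baseline qSOFA, fever duration (C1) and baseline host immune status. The qSOFA form in Appendix 1 D gives no time point, so say that the baseline score is meant. Host immune status need not be dropped.
3. Report outcome by identified infection descriptively: infections found by routine tests (the microbiology items M1 to M20, collected for all participants) in both arms, and infections found by the added serologies in Group B.

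The cost is a few sentences of text and a time label on the qSOFA form. No new tests, data items or patients are needed, and the sample size does not change.
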